1.15 Pathophysiology and molecular characteristics of pheochromocytomas and paragangliomas

Pheochromocytomas and paragangliomas are highly hypervascular tumors as suggested by immunohistochemical studies of vascular density (Liu, Djuricin et al. 1996; Ohji, Sasagawa et al. 2001). Quantitative as well as architectural differences between benign and malignant tumors have been demonstrated (Liu, Djuricin et al. 1996; Favier, Plouin et al. 2002; Zielke, Middeke et al. 2002). In addition, several angiogenic growth factors and their receptors are overexpressed in malignant pheochromocytomas and paragangliomas (Zielke, Middeke et al. 2002; Salmenkivi, Heikkila et al. 2003; Favier, Igaz et al. 2012). From these, vascular endothelium growth factor (VEGF), the most potent factor of vascular development, is the most studied, and consistent overexpression at both the genetic and protein expression level has been demonstrated (Favier, Plouin et al. 2002; Zielke, Middeke et al. 2002; Salmenkivi, Heikkila et al. 2003). Several other key angiogenic factors are also overexpressed such as the hypoxia induced transcription factor EPAS1, and the endothelin receptors type A (ETA) and type B (ETB) (Favier, Plouin et al. 2002). Anti-VEGF antibodies have been shown to

inhibit angiogenesis in experimental pheochromocytomas (Zielke, Middeke et al. 2002).

The genetics of pheochromocytomas and paragangliomas are very complex (Dahia 2006). Adrenal pheochromocytoma is strongly associated with multiple endocrine neoplasia 2A and 2B, von Hippel-Lindau disease (VHL), and familial paraganglioma syndrome (Neumann, Bausch et al. 2002; Boedeker, Ridder et al. 2005), and is less commonly seen with neurofibromatosis type 1 (NF 1) or MEN 1. However, malignant adrenal pheochromocytoma is only infrequently seen in association with these genetic syndromes. On the contrary, extra-adrenal malignant paragangliomas are most frequently seen in association with familial paraganglioma syndrome (PGL), an autosomal dominant disorder presenting with paragangliomas in the head and neck, but also in the thorax, abdomen, and urinary bladder (Neumann, Bausch et al. 2002; Boedeker, Ridder et al. 2005). Most cases are caused by mutations in the succinate dehydrogenase gene (SDH) subunits B, C and D even in apparent “sporadic” cases. Extra-adrenal malignant paraganglioma is strongly associated with mutations of the B subunit of the gene (SDHB) (Amar, Baudin et al. 2007).

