1.4 Hypotheses

Hypothesis 1: Lenvatinib treatment of patients with advanced malignant pheochromocytoma and paraganglioma may lead to attenuated tumor growth and/or tumor regression (as defined by RECIST criteria – see [Section 11.0](#)).

Hypothesis 2: Lenvatinib-induced changes in plasma and urinary catecholamine and/or metanephrine levels in patients with advanced, catecholamine secreting pheochromocytoma and paraganglioma may be observed and be predictive of patient objective response to lenvatinib therapy (per RECIST criteria – see [Section 11.0](#)).

Hypothesis 3: Somatic mutational status (presence of SDHD, SDHB, RET, VHL, neurofibromatosis type-1 in archival tumors) may predict response to lenvatinib therapy.

Hypothesis 4: Germline mutational status (detection of SDHD, SDHB, RET, VHL, neurofibromatosis type-1 in patient's PBMCs) may predict response to lenvatinib therapy.

Hypothesis 5: There is no significant deleterious net change in patient reported quality of life during lenvatinib therapy.

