Descriptive statistics, and scatter plots will form the basis of presentation of these data both overall and by other outcomes (toxicity, response and survival measures). Correlations between the QOL outcomes and other outcome measures will be carried out by standard parametric and non-parametric tests (e.g. Pearson's and Spearman's rho). Comparison between continuous variables will be made with Wilcoxon rank sum tests, Fisher's exact tests will be used to determine differences between categorical variables, and Log-rank test will be used to test differences between time-to-event outcomes.

16.23 Correlative aims:

16.231 For patients with secretory tumors

To examine changes in urinary catecholamine and metanephrine levels during treatment, time series plots of urinary catecholamines and metanephries levels will be constructed (with patient whose tumor responded to treatment in red and patients whose tumor remained stable or progressed in blue) to visually assess trends prior to treatment discontinuation within and between chemistries as well as difference in trends between those whose tumor responded to treatment and those whose tumor did not.

To examine whether lenvatinib-induced changes in urinary catecholamine and/or metanephrine levels during the first cycle of treatment may be associated with objective tumor response, the fold change from baseline levels for each biomarker will be determined. For each biomarker, a plot of the fold change versus response status will be constructed to visually assess differences between those whose tumor

responded to treatment and those whose tumor did not. If feasible, Wilcoxon rank sum tests will be used to examine whether fold changes in a given biomarker during the first cycle of treatment differs between those whose tumor responded to treatment and those whose tumor did not.

- 16.232 To examine associations between tumor response and somatic mutational status in archived tumors, or germline mutational status in patient's peripheral blood mononuclear cells, (presence of SDHD, SDHB, RET, VHL, neurofibromatosis type-1).
For SDHD, SDHB, RET, VHL, neurofibromatosis type-1, a 95% confidence interval for the difference in proportion of patients who have a documented tumor response among those with that particular biomarker present and proportion of patients who have a documented tumor response among those without that particular biomarker present.

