17.32 Methodology

We will investigate if the somatic mutations and germline mutations in paragangliomas and pheochromocytomas correlated with outcome data. FFPE collected at registration will be subjected to DNA extraction and analyzed for mutations in select genes using DNA sequencing.

Ten 5-micron unstained slides and 1 hematoxylin and eosin (H&E) stained slide will be cut from fresh frozen paraffin embedded (FFPE) tissue block. Pathologist will review slides and circle areas with adequate tumor tissue (>20%-40%). Circled H&E slide will serve as template for microdissection (using razor blade or scalpel) of unstained slides for DNA extraction. DNA extraction will be performed using Qiagen FFPE kit as per manufacturer's protocol. Approximately 30 ng of input DNA will be placed into a polymerase chain reaction. The Ion Ampliseq Cancer Hotspot Panel v2 primers (Life technologies) and Illumina MiSeq instrument will be used for gene sequencing. The mutations and genetic alterations identified will be correlated with reference to clinical data obtained during the conduct of the trial.

Germline mutation data will be collected from consenting patients and correlated with outcome data. If it is already performed we will obtain the report. If not performed, consultation will be performed with genetic counselor and germline testing obtained if consented and recommended.

Both of the above components, somatic mutational profile and germline testing are optional correlates.

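### The somatic-mutation contrast in Section 16.232 does not separate inherited from tumor-acquired variants, so it can appear to support Hypothesis 3 when only germline status is related to response

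*Combined protocol and SAP*

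**What the plan says.** Section 1.4 states two separate hypotheses on the same five genes. Hypothesis 3 reads "Somatic mutational status (presence of SDHD, SDHB, RET, VHL, neurofibromatosis type-1 in archival tumors) may predict response to lenvatinib therapy". Hypothesis 4 reads "Germline mutational status (detection of SDHD, SDHB, RET, VHL, neurofibromatosis type-1 in patient's PBMCs) may predict response to lenvatinib therapy". The only thing that distinguishes them is the specimen in which the variant is found.

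Section 17.32 describes the tumor assay: "FFPE collected at registration will be subjected to DNA extraction and analyzed for mutations in select genes using DNA sequencing". It continues: "The mutations and genetic alterations identified will be correlated with reference to clinical data obtained during the conduct of the trial". It describes no paired normal sample, no removal of inherited variants and no label of origin. Germline results come separately, from existing reports or from counselor-led testing. Tumor profiling and germline testing are both optional.

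Section 16.232 names the two sources together, "somatic mutational status in archived tumors, or germline mutational status in patient's peripheral blood mononuclear cells", and gives one method for both: a 95% confidence interval for the "difference in proportion of patients who have a documented tumor response among those with that particular biomarker present", compared with patients who lack it. It does not say how to class a variant found in both specimens. Section 12.7 records whether an inherited syndrome is present (yes, no or unknown), but 16.232 does not use that field.

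**The concern.** An inherited variant is carried in every cell, so sequencing the tumor will find it there as well. The background makes such patients likely in this trial. Section 1.15 describes familial paraganglioma syndrome as "an autosomal dominant disorder presenting with paragangliomas in the head and neck" and elsewhere in the body, and attributes most cases to SDH mutations, including cases that look sporadic. It also ties SDHB strongly to malignant extra-adrenal disease.

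Under the stated definition, germline carriers enter the group counted as somatic-positive. If germline status is related to response, as Hypothesis 4 proposes, the interval reported for Hypothesis 3 will tend to show the same signal even when acquired mutations have no effect. One observation in one set of patients could then be presented as two supportive findings. With at most 23 eligible patients in the decision rule, a choice of classification made after the data are seen could also change the result.

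**Working it through.** **Plan's own figure.** Section 16.232 gives no power, carrier rate or response rate by genotype, so there is nothing to reproduce for this aim. The two-stage table in Section 16.13 does reproduce (0.149, 0.368, 0.585, 0.748 and 0.852 for true rates of 10% to 30%), but this point does not rest on it.

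**Inputs.** From the documents: a maximum of 23 eligible patients (16.122) and a 95% interval for a difference in proportions (16.232). Assumed, because the documents are silent:
- germline carriers of one gene, g = 25% or 40%
- acquired variants with no effect, in a = 5% of non-carriers
- 12, 18 or 23 patients with data
- response p_C in germline carriers and p_N in everyone else
- the Newcombe interval, since no method is named

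**Step 1: what the tumor contrast estimates.** The tumor-positive group mixes germline carriers and acquired-variant carriers, so its expected difference from the rest is

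[g·p_C + a(1−g)·p_N] / [g + a(1−g)] − p_N.

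At 50% versus 15%:
- g = 0.25: (0.125 + 0.0375×0.15)/0.2875 − 0.15 = 0.454 − 0.15 = 0.304
- g = 0.40: (0.200 + 0.03×0.15)/0.43 − 0.15 = 0.476 − 0.15 = 0.326

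The contrast labelled somatic thus carries 30 to 33 of the 35 points of germline effect, although the acquired variants do nothing.

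**Step 2: how often the interval excludes zero.** With Wilson limits (l, u) for each group and d = p1 − p2, the Newcombe limits are d − √[(p1−l1)² + (u2−p2)²] and d + √[(u1−p1)² + (p2−l2)²]. Simulation, 20,000 trials per scenario, ranges over the two values of g:

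| Patients | 50% vs 15% | 60% vs 10% |
|---|---|---|
| 12 | 22-23% | 39-43% |
| 18 | 31-33% | 53-60% |
| 23 | 35-40% | 61-70% |

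With 30% response in everyone, the figure is 4.5-5.2%. The excess therefore comes from the germline effect and not from the interval method.

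**Step 3: exact check with fixed group sizes (23 patients, 50% versus 10%).** With 6 germline carriers and no acquired variants, the tumor and germline contrasts compare the same patients. Each interval lies wholly above zero with probability 0.514. Adding 3 patients with inert acquired variants lowers the tumor figure to 0.373. With 30% response in everyone, the tumor figures for these two group structures are 0.025 and 0.033, near the nominal one-sided 0.025.

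**Step 4: what remains after germline carriers are removed.** The chance that a trial has no somatic-only carrier is [1 − a(1−g)]^N:
- g = 0.25, N = 23: 0.9625^23 = 0.415
- g = 0.40, N = 12: 0.97^12 = 0.694

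The somatic-only contrast can therefore be computed in only about 31-59% of trials. Zero or one carrier is present in 79-95% of trials:
- 0.415 + 23×0.0375×0.9625^22 = 0.79
- 0.694 + 12×0.03×0.97^11 = 0.95

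Among trials where it can be computed, the interval excludes zero in about 4-8%.

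**The case against.** The strongest reply is that the plan is only silent. It names somatic and germline status as different things, collects them in separate streams, and nowhere forbids matching one to the other. A reader might infer that the plan orders inherited variants to be counted as somatic, and no section says so. What remains is that the one definition given is presence in the tumor, with no step that separates origin. An analyst who follows it will mix the two.

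A reader might also infer that the trial tests a null hypothesis and would confirm Hypothesis 3 in error, or that the null is a joint one across tumor and germline variants. The documents do not support this. Section 16.232 is a correlative aim that reports an interval, with no test and no confirmation rule, and Hypothesis 3 is worded as a possibility. The value implied by the interval is equal response with and without a tumor variant, gene by gene. The analysis does match the hypothesis's own operational definition. The fault lies in the word somatic and in what would be inferred from it.

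The magnitudes are wholly assumed, including a large germline effect and a high carrier rate for a single gene. That objection stands, and the figures are not estimates for this trial.

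Finally, restricting to germline-negative patients might seem to give a well-behaved error rate of 2-4%. That figure counts trials in which the contrast cannot be computed as not excluding zero, so it partly reflects an empty comparison.

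**Conclusion.** The point holds as one of classification and labelling. As defined, the somatic interval for a gene compares patients with and without a tumor variant of any origin. If only germline status is related to response, it can appear to support Hypothesis 3. If no patient has an acquired variant in that gene and the same patients have both tests, it duplicates the Hypothesis 4 contrast exactly.

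Under the assumptions listed above, the interval excludes zero several times more often than the roughly 5% seen with no genotype effect. How large the problem is here depends on carrier and response rates that the documents do not give. The consequence is confined to a correlative aim: the primary endpoint and the two-stage decision rule are not touched.

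**What to change.** In Section 16.232, label each tumor variant as one of:
- **germline**: the same variant is in the patient's germline report
- **somatic only**: the patient is germline-negative for that gene
- **origin unknown**: germline was not tested

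Then:
- report the plain tumor contrast as any tumor variant, origin not separated, and cross-tabulate it with germline status
- report the germline contrast among germline-tested patients
- base any statement about somatic status only on germline-negative patients, and present it descriptively

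The cost is a few sentences and one derived variable. It uses the germline results already planned under Section 17.32. The downside is that tissue and germline testing are both optional, so some origins will stay unknown and the somatic-only comparison will often be empty or rest on a single carrier. The plan should say so in advance.

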16.3 Reporting and Exclusions

- 16.31 Evaluation of adverse events.

All subjects will be evaluable for adverse events from the time of their first treatment with lenvatinib.

- 16.32 Evaluation of response.

All subjects included in the study must be assessed for response to treatment, even if there are major protocol treatment deviations or if they are ineligible. Each subject will be assigned one of the following categories: 1) complete response, 2) partial response, 3) stable disease, 4) progressive disease, 5) early death from malignant disease, 6) early death from toxicity, 7) early death because of other cause, or 9) unknown (not assessable, insufficient data). [Note: By arbitrary convention, category 9 usually designates the “unknown” status of any type of data in a clinical database.]

All of the subjects who met the eligibility criteria (with the possible exception of those who received no study medication) should be included in the main analysis of the response rate. Subjects in response categories 4-9 should be considered to have a treatment failure (disease progression). Thus, an incorrect treatment schedule or drug administration does not result in exclusion from the analysis of the response rate. Precise definitions for categories 4-9 will be protocol specific.

All conclusions should be based on all eligible subjects. Subanalyses may then be performed on the basis of a subset of subjects, excluding those for whom major protocol deviations have been identified (e.g., early death due to other reasons, early discontinuation of treatment, major protocol violations, etc.). However, these subanalyses may not serve as the basis for drawing conclusions concerning treatment efficacy, and the reasons for excluding subjects from the analysis should be clearly reported. The 95% confidence intervals should also be provided.

16.4 Monitoring

The principal investigator and the study statistician will review the study periodically to identify accrual, toxicity, and any endpoint problems that might be developing. In addition, this study will be monitored according to the Mayo Clinic Cancer Center (MCCC) Data Safety Monitoring Plan that is currently in place. The MCCC Data Safety Monitoring Board (DSMB) is responsible for reviewing safety data for this trial at least twice a year, based on reports provided by the MCCC Statistical Office.

16.41 Adverse Event Stopping Rules

NOTE: NCI CTCAE v4.0 will be used to determine grading for adverse event stopping rules.

If 2 or more of the first 5 patients enrolled or 30% or more of the patients enrolled thereafter develop a grade 4 or severer non-hematologic toxicity (except for hypertension) or grade 4 or severer hematologic toxicity that are considered possibly, probably, or definitely related to treatment, enrollment to the study will be suspended. The study team will review all adverse event data. A trial recommendation will be formulated and presented to the MCCC DSMB – the study may permanently close or may re-open to accrual after CTEP and IRB approvals of protocol/consent form modifications.

16.5 Results Reporting on ClinicalTrials.gov

At study activation, this study will have been registered within the “ClinicalTrials.gov” website. The Primary and Secondary Endpoints along with other required information for this study will be reported on www.ClinicalTrials.gov. For purposes of timing of the Results Reporting, the initial estimated completion date for the Primary Endpoint of this study is 3 years after the study opens to accrual. The definition of “Primary Endpoint Completion Date” (PECD) for this study is at the time the last patient registered has been followed for at least 6 months.

16.6 Subset Analyses for Minorities:

16.61 Study availability

This study will be available to all eligible patients, regardless of gender, race or ethnic origin.

16.62 Statistical analysis by subset

There is no information currently available regarding differential effects of this regimen in subsets defined by race, gender, or ethnicity, and there is no reason to expect such differences to exist. Therefore, although the planned analyses will look for differences in treatment effect based on racial groupings, the sample size is not increased in order to provide additional power for subset analyses.

16.63 Regional population

The geographical region served by MCCC has a population which includes approximately 3% minorities. Based on prior MCCC studies involving similar disease sites, we expect about 3-5% of patients will be classified as minorities by race and about 33% of patients will be women. Expected sizes of racial by gender subsets are shown in the following table:

Accrual Targets			
Ethnic Category	Sex/Gender		
	Females	Males	Total
Hispanic or Latino	0	1	1
Not Hispanic or Latino	12	12	24
Ethnic Category: Total of all subjects	12	13	25
Racial Category			
American Indian or Alaskan Native	0	0	0
Asian	1	1	2
Black or African American	0	1	1
Native Hawaiian or other Pacific Islander	0	0	0
White	11	11	22
Racial Category: Total of all subjects	12	13	25

- Ethnic Categories:** **Hispanic or Latino** – a person of Cuban, Mexican, Puerto Rican, South or Central American, or other Spanish culture or origin, regardless of race. The term “Spanish origin” can also be used in addition to “Hispanic or Latino.”
- Not Hispanic or Latino**
- Racial Categories:** **American Indian or Alaskan Native** – a person having origins in any of the original peoples of North, Central, or South America, and who maintains tribal affiliations or community attachment.
- Asian** – a person having origins in any of the original peoples of the Far East, Southeast Asia, or the Indian subcontinent including, for example, Cambodia, China, India, Japan, Korea, Malaysia, Pakistan, the Philippine Islands, Thailand, and Vietnam. (Note: Individuals from the Philippine Islands have been recorded as Pacific Islanders in previous data collection strategies.)
- Black or African American** – a person having origins in any of the black racial groups of Africa. Terms such as “Haitian” or “Negro” can be used in addition to “Black or African American.”
- Native Hawaiian or other Pacific Islander** – a person having origins in any of the original peoples of Hawaii, Guam, Samoa, or other Pacific Islands.
- White** – a person having origins in any of the original peoples of Europe, the Middle East, or North Africa.

17.0 PATHOLOGY CONSIDERATIONS/TISSUE BIOSPECIMENS

17.1 Summary Table of Research Tissue Specimens to be collected for this Protocol

Collection (Section for more information)	Mandatory or Optional	Type of Tissue to Collect	Block, Slides, Core, etc. (# of each to submit)	≤42 days after Registration	Process at site? (Yes or No)	Temperature Conditions for Storage /Shipping
Tumor tissue for correlative studies (Section 17.3)	Optional	Formalin Fixed Paraffin embedded	FFPE Block or 10 unstained FFPE slides (5 micron) and 1 FFPE slide stained with hematoxylin and eosin (H&E)	X	Yes	Ambient

17.2 Correlative Tissue Collection (Optional)

17.21 Tissue Kits will not be provided for this protocol.

17.22 Paraffin Embedded Tissue

17.221 Submit one formalin fixed paraffin-embedded (FFPE) tumor tissue block (if available) with largest amount of invasive tumor (at least 1 cm of tumor for cases of surgical resection) from metastatic tumor biopsy.
Or 10 unstained FFPE slides (5 micron), and 1 FFPE slide stained with hematoxylin and eosin. Do not coverslip unstained slides.

17.222 Send to attention of:

17.223 Store at room temperature

